### **3.1.12 Optional Study Treatment Extension**

Treatment extension with nivolumab monotherapy beyond 18 weeks is permitted and will be managed at the Investigator's discretion in accordance with standard practice. Subjects who require additional treatment will continue to be followed for efficacy assessments and On Study Follow-up (see Section 3.1.16 and Section 3.2). Details of extended nivolumab monotherapy administration should be captured on the Drug Administration electronic case report form (eCRF).

### **3.1.13 Interim Analysis**

An interim analysis of safety will be performed after 9 subjects in Cohort A have completed concurrent ipilimumab and nivolumab therapy in order to determine whether to proceed with enrollment into Cohort B (see Section 3.1).

### **3.1.14 Safety Monitoring and Study Stopping Rules**

In accordance with the Administrative, Legal and Ethical Requirements section of the protocol (see Section 7), Safety Monitoring will be performed by an internal data safety monitoring panel, consisting of the Principal Investigators (and co-investigators as needed), the Sponsor's medical

monitor, and drug safety personnel from Bristol-Myers Squibb, the provider of the study drugs. Additional investigators and staff, or additional Sponsor personnel and consultants, shall participate in reviews as indicated. An Independent Data Monitoring Board will not be utilized for this open-label study.

The study will be suspended or possibly stopped prematurely for any of the following reasons:

1. A death that is unexpected and at least probably related to 1 or more of the study drugs and/or RT.
2. Severe anaphylactic reaction (i.e., with respiratory and cardiovascular failure) to 1 or more of the study drugs.
3. Any events that, in the judgment of the medical monitor, are deemed serious enough to warrant immediate review by the data safety monitoring panel.
4. Any other safety finding assessed as related to 1 or more study drugs that, in the opinion of the internal data safety monitoring panel, contraindicates further dosing of study subjects.
5. Any interim findings that, in the opinion of the Investigators and the Sponsor, suggest that the study treatment has no clinical benefit for the subjects.

General criteria for premature trial termination are outlined in the Administrative Section 7.

### **3.1.15 Duration of Study**

Duration of Treatment:	1 year (subjects benefitting from nivolumab treatment may receive continued treatment)
Enrollment Period:	2 years
Length of Study:	3 years
Length of Survival Follow-up	3 years

### **3.1.16 On Study and Post-Study Follow-up**

All subjects, whether they complete the study as planned, discontinue treatment, or prematurely withdraw from the study as per Section 3.1.10, will be followed as per institutional guidelines in accordance with the usual standard of care principles.

On Study Follow-up will be conducted for 100 days after the last study drug administration according to the flowchart in Section 3.2. Refer to Section 7.1.5 for information on recording AEs during the On Study Follow-up.

In addition to the On Study Follow-up, there will be a Post Study Follow-up, during which clinical outcomes data (dates of progression/relapse and survival) will be collected at least every 12 ( $\pm$  1) weeks for 3 years after completion of 100-day On Study Follow-up. For subjects who do not continue Post Study Follow-up at one of the study sites after the end of study, the Principal Investigators or the clinical team, under the supervision of the Principal Investigator, will obtain the data through review of outside records or communication with the subject or his/her physician.

### 3.2 Study Flowchart

Study Section	Screening	Treatment								Final Assessment and Ongoing Treatment/ Assessments d	On Study Follow-up a,e	Post-Study Follow-up (Section 3.1.16)
		Week 1 (Cycle 1)	Week 4 (Cycle 2)	Week 7 (Cycle 3)	Week 10 (Cycle 4)	Week 12	Week 14	Week 16	Week 18			
Study Week												
Study Day	-28 to 0 (or as stated)	1	22 (± 3)	43 (± 3)	64 (± 3)	78 (± 3)	92 (± 3)	106 (± 3)	120 (± 3)	2 weeks (± 3 days) after last study drug	30 (±4), 70 (±4) and 100-107 days after last study drug (AEs and pregnancy tests)	(Starts after completion of 100-day On Study Follow-up) Q12W (± 7 d) for 3 years
Drug Administration Cohort A												
Ipilimumab f IV		X	X	X	X							
Nivolumab f IV		X	X	X	X	X	X	X	X	X d		
Radiotherapy b,f (30 Gy over 10 fractions of 3 Gy)		X										
Drug Administration Cohort B												
Ipilimumab f IV		X	X	X	X							
Nivolumab f IV		X	X	X	X	X	X	X	X	X d		
Radiotherapy b,f (27 Gy over 3 fractions of 9 Gy)		X										
Tumor & Disease Assessments												
Disease Staging (date/stage at first diagnosis and study entry)	X											
Disease Assessment by RECIST 1.1 and irRECIST	X					X			X	X d (Week 24, then Q12W ± 7 days)		
Other Procedures & Examinations												
Eligibility Assessment and Informed Consent	X											
Demographics (including DoB, sex, height, race, ethnicity)	X											
Medical History	X											
Physical Exam (including weight)	X	X	X	X	X	X	X	X	X	X d		

CONFIDENTIAL

Study Section	Screening	Treatment								Final Assessment and Ongoing Treatment/ Assessments d	On Study Follow-up a,e	Post-Study Follow-up (Section 3.1.16)
		Week 1 (Cycle 1)	Week 4 (Cycle 2)	Week 7 (Cycle 3)	Week 10 (Cycle 4)	Week 12	Week 14	Week 16	Week 18			
Study Week	Study Day	1	22 (± 3)	43 (± 3)	64 (± 3)	78 (± 3)	92 (± 3)	106 (± 3)	120 (± 3)	2 weeks (± 3 days) after last study drug	30 (±4), 70 (±4) and 100-107 days after last study drug (AEs and pregnancy tests)	(Starts after completion of 100-day On Study Follow-up) Q12W (± 7 d) for 3 years
Electrocardiogram (baseline and as clinically indicated)	X											
Vital Signs (temperature, HR, BP, RR)	X	X	X	X	X	X	X	X	X	X d		
ECOG Performance Status	X	X	X	X	X	X	X	X	X	X d		
Concomitant Medications/Procedures	X	X	X	X	X	X	X	X	X	X d		
Adverse Events Assessment	X	X	X	X	X	X	X	X	X	X d	X	
Laboratory Measurements & Assays												
Serum Pregnancy Test e	X									X d,e	X e	
Urine Pregnancy Test (collected pre-dose) e		X		X		X			X	(Q6W) d,e		
Chemistry (Na, K, Cl, CO 2 , BUN, creat., gluc., Ca, Mg, total prot., alb., Tbili., AST, ALT, ALP, LDH; blood drawn before dosing) g	(-14 to 0) X	X	X	X	X	X	X	X	X	X d,g		
Free T 3 , Free T 4 , TSH; blood drawn before dosing g	(-14 to 0) X	X	X	X	X	X	X	X	X	X d,g		
Amylase, lipase; blood drawn before dosing	(-14 to 0) X	X	X	X	X	X	X	X	X	X d		
Blood Hematology (CBC with differential and platelets; blood drawn before dosing)	(-14 to 0) X	X	X	X	X	X	X	X	X	X d		
Research Blood Draw (60 mL; blood drawn before dosing)		X		X		X						
Tumor Biopsy (optional) c	X	X		X	X	X	X	X	X			

CONFIDENTIAL

Study Section	Screening	Treatment								Final Assessment and Ongoing Treatment/ Assessments d	On Study Follow-up a,e	Post-Study Follow-up (Section 3.1.16)
		Week 1 (Cycle 1)	Week 4 (Cycle 2)	Week 7 (Cycle 3)	Week 10 (Cycle 4)	Week 12	Week 14	Week 16	Week 18			
Study Week												
Study Day	-28 to 0 (or as stated)	1	22 (± 3)	43 (± 3)	64 (± 3)	78 (± 3)	92 (± 3)	106 (± 3)	120 (± 3)	2 weeks (± 3 days) after last study drug	30 (±4), 70 (±4) and 100-107 days after last study drug (AEs and pregnancy tests)	(Starts after completion of 100-day On Study Follow-up) Q12W (± 7 d) for 3 years
Progression and Survival Follow-up												X

Abbreviations: alb. = albumin; ALP = alkaline phosphatase; ALT = alanine aminotransferase; AST = aspartate aminotransferase; Tbili. = total bilirubin; BP = blood pressure; BUN = blood urea nitrogen; Ca = calcium; CBC = complete blood count; Cl = chloride; CO2 = carbon dioxide; creat. = creatinine; CT = computed tomography; d = day(s); DoB = date of birth; ECOG = Eastern Cooperative Oncology Group; eCRF = electronic case report form; gluc. = glucose; Gy = Gray; HR = heart rate; irRECIST = immune-related RECIST; IV = intravenous(ly); K = potassium; mL = milliliter(s); LDH = lactate dehydrogenase; Mg = magnesium; Na = sodium; prot. = protein; Q = every; RECIST = Response Evaluation Criteria for Solid Tumors; RR = respiratory rate; RT = radiotherapy; W = week(s); Q6W = every 6 weeks; Q12W = every 12 weeks

Note: Additional assessments may be evaluated at the Investigator's discretion and per standard of care. Indicated assessments within this chart define clinical data to be captured in the eCRF. Standard of Care procedures may be used for eligibility assessments, provided they meet the criteria specified in either the inclusion criteria or flowchart.

a Subjects will be followed for 100 days after the last dose of study drug as a part of On Study Follow-up; during this time, all AEs will be collected at 30 (±4), 70 (±4) and 100-107 days.

b Radiotherapy will be delivered by standard or high dose palliative RT as per cohort assignment.

c Tumor biopsies are optional but are encouraged. Biopsies are prohibited from compromising the requirement for at least one measurable lesion not undergoing RT.

d **Final Assessment** will be 2 weeks (± 3 days) after last study drug, followed by On Study Follow-up and Post Study Follow-up. A repeat disease assessment scan is not required at the final assessment visit if a scan was done within the previous 6 weeks before the final assessment visit. Subjects who do not continue treatment with nivolumab after Week 18 do not need to have a repeat pregnancy test (if applicable) at the final assessment if the subject had this assessment at Week 18.

**For those subjects who are continuing on nivolumab after Week 18 at 240 mg every 2 weeks ±3 days**, Study Visits will continue every 2 weeks ± 3 days during treatment, followed by the Final Assessment Visit, On Study Follow-up, and Post Study Follow-up after the last nivolumab treatment.

Per Amendment 5, nivolumab monotherapy continuing after Week 18 may be given as 480 mg every 4 weeks ±3 days, starting on Week 20, followed by Weeks 24, 28, etc.

**For those subjects who are continuing on nivolumab after Week 18 at 480 mg every 4 weeks ±3 days**, Study Visits will continue every 4 weeks ± 3 days during treatment, followed by the Final Assessment Visit, On Study Follow-up, and Post Study Follow-up after the last nivolumab treatment.

Subjects continuing nivolumab monotherapy, subjects who complete study treatment as responders, and subjects who have not progressed (either in irradiated or non-irradiated tumor burden) will have an additional scan (disease assessments by RECIST 1.1/ irRECIST) at Week 24 and subsequent scans Q12W (± 7 days) until progression or start of alternate anti-cancer therapy.

e For females of child-bearing potential (as defined in Section 5.2), pregnancy tests required every 6 weeks and repeated at 30 (±4) days and 70 (±4) days after discontinuation of treatment. Serum pregnancy test is done at screening, final assessment, and during On Study Follow-up; urine pregnancy test is done at all other visits, including during continued nivolumab treatment (Note: For females of child-bearing potential who are continuing on nivolumab after Week 18 at 480 mg every 4 weeks, urine pregnancy tests may be done every 8 weeks). Urine pregnancy test is done and results confirmed pre treatment on Day 1 of study.

f All subjects will receive concurrent nivolumab (1 mg/kg) followed by ipilimumab (3 mg/kg) on the same day every 3 weeks for 4 doses, then followed by nivolumab monotherapy (240 mg every 2 weeks ±3 days) See footnote d for ongoing nivolumab monotherapy after Week 18. Radiotherapy will be initiated after the first dose and before the second dose of immunotherapy.

g Per Amendment 5: After Week 18, LDH testing and TSH (with reflexive free T3/T4) testing during ongoing nivolumab treatment will be done as clinically indicated; other testing will continue per flowchart.

CONFIDENTIAL

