## **4.2 Clinical Efficacy**

### **4.2.1 Endpoints & Assessment Methods**

Clinical efficacy will be determined by objective response rate (ORR), disease control rate (DCR), duration of response, progression-free survival (PFS), and overall survival (OS). The primary method of assessment of tumor response will be the Response Evaluation Criteria for Solid Tumors (RECIST) 1.1, and the secondary method of response evaluation will be irRECIST (see Section 8.4)

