#### **4.2.1.4 Progression-free Survival**

PFS will be defined as the number of days from the date of the first dose of study drug to the date of earliest disease progression based on the appropriate response evaluation method, or to the date of death, if disease progression does not occur. Subjects who do not progress and are still alive will be censored on the date of last follow-up or start of new treatment, whichever comes first. Every effort will be made to follow subjects for progression after they discontinue the study.

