### II Follow-up Assessments in irRECIST

#### *A. Follow-up recording of target and new measurable lesions*

**A key difference in irRECIST is that the appearance new lesions does not automatically indicate progression. Instead, all measured lesions (baseline-selected target lesions and new measurable lesions) are combined into the total measured tumor burden (TMTB) at follow up. Baseline-selected target lesions and new measurable lesions are NOT assessed separately. Measurements of those lesions are combined into the TMTB, and one combined assessment provided.**

In order to be selected as new measurable lesions ( $\leq 2$  lesions per organ,  $\leq 5$  lesions total, per time point), new lesions must meet criteria as defined for baseline target lesion selection and meet the same minimum size requirements of 10 mm in long diameter and minimum 15 mm in short axis for new measurable lymph nodes. New measurable lesions should be prioritized according to size, and the largest lesions elected as new measured lesions.

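### The scan-stop rule after Week 18 does not say which criterion defines progression, so any irRECIST PFS or duration of response can be overstated

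*Combined protocol and SAP*

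**What the plan says.** - **Who is scanned after Week 18.** Footnote d to the flowchart (3.2) lists "Subjects continuing nivolumab monotherapy, subjects who complete study treatment as responders, and subjects who have not progressed". These subjects "will have an additional scan (disease assessments by RECIST 1.1/ irRECIST"), and the schedule runs "at Week 24 and subsequent scans Q12W (± 7 days) until progression or start of alternate anti-cancer therapy". No criterion is attached to the stop.
- **What is recorded.** The flowchart note says: "Indicated assessments within this chart define clinical data to be captured in the eCRF". Anything further is at the investigator's discretion and per standard of care.
- **Which method leads.** Section 4.2.1 states "The primary method of assessment of tumor response will be the Response Evaluation Criteria for Solid Tumors (RECIST) 1.1". On the immune-related criteria it adds only that "the secondary method of response evaluation will be irRECIST".
- **How the methods differ.** In Section 8.4 a new lesion is progression under RECIST 1.1. Under irRECIST "the appearance new lesions does not automatically indicate progression"; measurable new lesions are instead added to the total measured tumor burden.
- **Endpoints.** Section 4.2.1.4 counts the earliest progression by whichever response method is appropriate, and then: "Subjects who do not progress and are still alive will be censored on the date of last follow-up or start of new treatment", whichever is earlier. Section 4.2.1.3 names no method for duration of response and gives no censoring rule. The objectives table in Section 4 attaches both methods to ORR and DCR only.
- **Treatment.** Under Section 3.1.10, radiographic progression is a reason to stop study treatment only where it warrants alternative treatment.

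**The concern.** The protocol adopts irRECIST because response can follow an apparent increase in disease (8.4). That information comes only from scans taken after RECIST 1.1 has already called progression. If the required scans end at that call, the irRECIST course of the subjects for whom the two methods disagree is left largely unobserved.

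The censoring rule then matters. A subject who is alive, on no new treatment and not scanned has no recorded irRECIST progression. Censoring at last follow-up credits that subject with progression-free time that nobody has looked at. An irRECIST PFS curve would sit too high, and an irRECIST duration of response would run too long.

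**Working it through.** The plan gives no event count, power or precision for PFS or duration of response, so there is no figure to reproduce. The check is a comparison of the text, followed by an illustration of size.

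**Text**

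1. *Can the methods disagree?* Yes. A new lesion that does not raise the total measured tumor burden by at least 20% and 5 mm over nadir, and is not massive unequivocal worsening, is progression under RECIST 1.1 but not under irRECIST (8.4). Call this RECIST-only progression.
2. *Can it go the other way?* Not on the rules as summarised in 8.4. Each route to irRECIST progression (tumor burden, non-target lesions, new lesions) already meets a RECIST 1.1 progression rule. Scanning to irRECIST progression therefore loses nothing for RECIST 1.1.
3. *Can nivolumab continue after RECIST-only progression?* Yes (3.1.10).
4. *What imaging is still required then?* If progression is read literally, or as RECIST 1.1, the 12-weekly scans end. A Final Assessment scan remains, 2 weeks after the last dose, unless one was done in the previous 6 weeks. A subject whose last dose falls within about 6 − 2 = 4 weeks of the RECIST progression scan therefore needs no further scan. One treated for longer needs a single scan at the end.
5. *Does later follow-up fill the gap?* Section 3.1.16 collects progression dates at least every 12 weeks for 3 years after the 100-day follow-up, with outside records allowed. It requires no scan and names no criterion. irRECIST progression generally depends on measured tumor burden, which a reported date does not supply.

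**Size**

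From the protocol: scans at Weeks 12, 18 and 24, then every 12 weeks; 18 subjects. Assumptions not in the documents:

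- exponential RECIST 1.1 PFS with median 26 or 50 weeks;
- 0-30% of progressions RECIST-only;
- 50% or 100% of these reach irRECIST progression at the next scan, and the rest after a median of 52 further weeks;
- last follow-up at Week 156;
- no deaths, new treatment, Final Assessment scan or other later capture of irRECIST progression.

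The Week 18 scan is kept for everyone. Kaplan-Meier irRECIST PFS at Week 48 was compared with its value under full scanning (100,000 simulated subjects per scenario). Ranges cover both medians and both shares.

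| RECIST-only share | Affected, of 18 | Overstatement, censored at RECIST progression scan (points) | Overstatement, censored at last follow-up (points) |
|---|---|---|---|
| 0% | 0 | 0 | 0 |
| 10% | 1.3-1.6 | 0.6-2.1 | 1.8-3.4 |
| 20% | 2.6-3.3 | 1.5-4.6 | 3.6-6.9 |
| 30% | 3.9-4.9 | 3.0-7.2 | 5.2-10.2 |

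The estimated median moves by 0 to 24 weeks, that is, 0 to 2 scan intervals.

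The largest case (median 26 weeks, 30%, all reaching irRECIST progression at the next scan) can be checked by hand. With S(t) = 2^(−t/26): S(12) = 0.7262, S(36) = 0.3830, S(48) = 0.2781.

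- Full scanning: S(48) plus the RECIST-only progressors first seen at Week 48 = 0.2781 + 0.3 × (0.3830 − 0.2781) = 0.310 (simulated 0.311).
- Censored at last follow-up: RECIST-only progressors first seen after Week 12 and up to Week 48 all count as progression-free. 0.2781 + 0.3 × (0.7262 − 0.2781) = 0.413 (simulated 0.413).
- Difference: about 10 points.

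For scale, the binomial standard error at 0.311 with 18 subjects is √(0.311 × 0.689 / 18) = 0.109. The 95% half-width is about 1.96 × 0.109 = 0.21, or 21 points.

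Duration of response was not simulated. Its direction follows from the same mechanism: the end of an irRECIST response goes unseen after a RECIST-only progression.

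**The case against.** The case against is substantial, and most of it limits the point rather than removing it.

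- **RECIST 1.1 is not named as the stop.** A reader might infer that it is, because 4.2.1 makes it primary. That sentence concerns assessment of tumor response, and footnote d cites both methods. Scanning until progression by each method is also an available reading. This stands. The defect is that the text leaves the choice open at three sites.
- **Subjects are not simply lost to imaging.** Those continuing nivolumab are listed separately from those who have not progressed, and a Final Assessment scan may follow. This stands in part: the listing governs entry to the schedule, but the same sentence ends the schedule at progression for all three groups.
- **The plan does not censor at RECIST progression.** A reader might describe this as informative censoring at that date. Section 4.2.1.4 says last follow-up or new treatment. The correction stands, but the bias under that rule is larger in every scenario with any RECIST-only progression.
- **irRECIST PFS and duration of response are only implied.** This also stands. Section 4.2.1 covers all the efficacy endpoints under both methods, but no list names these two by irRECIST.
- **The consequence is small.** These are descriptive secondary endpoints in 18 subjects, no decision rule uses them, and even the largest shift is about half the 95% half-width. This stands and sets the severity.

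**Conclusion.** The point holds in a limited form and is minor. Footnote d leaves the stopping criterion open. On a literal or RECIST 1.1 reading, required 12-weekly imaging can end before irRECIST progression or response can be seen. Combined with censoring at last follow-up, this biases any reported irRECIST PFS or duration of response upward.

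At Week 48 the PFS overstatement is about 0.6 to 7 points with censoring at the RECIST progression scan. It reaches about 10 points with censoring at last follow-up if no later irRECIST progression is captured. These sizes rest on the assumed 10-30% RECIST-only share and the assumed timing of later progression. At 0% there is no bias. Deaths (which are PFS events) and any progression captured later would reduce the last-follow-up figures.

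The documents do not support saying that the plan makes RECIST 1.1 the stopping trigger or that these subjects are never scanned again. ORR and DCR at Weeks 12 and 18 are unaffected, because those scans are scheduled for all subjects.

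**What to change.** 1. **Footnote d (3.2).** State that study scans for endpoint assessment continue until irRECIST progression, or until another anti-cancer treatment begins. This concerns imaging for the endpoints only and leaves the treatment rules as they are.
2. **Sections 4.2.1.3 and 4.2.1.4.** State that PFS and duration of response are reported by each method. Censor subjects without progression at their last evaluable disease assessment, keeping the existing cut at new treatment.

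Both changes are needed. Censoring at the last evaluable scan alone would still leave the 0.6 to 7.2 points in the table's third column, because the missing scans would still be missing.

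A sensitivity analysis that counts the RECIST-only date as an irRECIST event is not worth adding. It would simply give those subjects their RECIST 1.1 PFS time, which the primary method already reports.

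The cost is a few sentences and a few more 12-weekly scans in RECIST-only progressors. Section 4.2.1.1.1 already regards imaging in subjects on these drugs as standard of care. Scans not taken cannot be recovered at analysis.

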## 4 Study Objectives & Endpoints

Primary Objective [Endpoints]	Safety and Tolerability [According to the NCI CTCAE, Version 4.03]
Secondary Objectives [Endpoints]	
 
• ORR by RECIST 1.1 and irRECIST [ORR at Weeks 12 and 18]
 
• DCR by RECIST 1.1 and irRECIST [DCR at Weeks 12 and 18]
 
• Duration of response
 
• PFS
 
• OS
 

Exploratory Objectives [Endpoints]	Antitumor Immunity [Immunological Effects of Ipilimumab/Nivolumab/RT]

CTCAE = National Cancer Institute Common Terminology Criteria for Adverse Events; DCR = disease control rate; irRECIST = immune-related RECIST; ORR = objective response rate; OS = overall survival; PFS = progression-free survival; RECIST = Response Evaluation Criteria in Solid Tumors; RT = radiotherapy

